3.1.2. Rationale for study design

A single cohort study was chosen to estimate the incidence of dengue in the community. Data will be collected from a population of individuals aged 6 months and older for maximum four dengue seasons. Inclusion of individuals of various ages will further allow for a better understanding of disease dynamics, clinical spectrum, and validate attack rates for potential subgroups to be included in future dengue vaccine trials.

This study will use cluster (household) sampling to take into account the correlation that may exist within households. Individuals within a household are expected to have a more similar risk of infection compared to individuals from different households. For example, individuals living in the same household are more likely to share similar risk of being exposed to DENV infected mosquitoes. The sample size has been adjusted to account for this between-cluster variability.

A possible bias *may arise from the* non-response rate. *To reduce the possibility of this potential bias, visits will be scheduled* on weekends or at times *more convenient to the subject*. Where applicable, FHP community health care workers will facilitate communication between study staff and participants.

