3.2. Secondary objectives

- To estimate the serotype-specific incidence of virologically-confirmed symptomatic dengue infection in the study population overall and by season.
- To estimate the incidence of symptomatic dengue infection (including laboratory-confirmed and probable cases) in the study population by study site, gender, age-group, previous dengue exposure (primary or secondary), overall and by season.
- To estimate the prevalence of previous dengue infection (dengue seroprevalence) in the study population overall and by study site, gender and age-group at enrolment.
- To estimate the incidence of primary inapparent dengue infection, in the study population overall and by study site, gender age-group and by season.
- To describe symptoms and spectrum of dengue disease in the study population.

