7. STATISTICAL ANALYSES

Note that data derivation rules are described in Section 11 and will not be repeated below.

Continuous variables will be summarized with number of non-missing observations, mean, standard deviation (SD), median, minimum, maximum, 25th and 75th percentiles. Categorical variables will be summarized with frequency tables; numbers and percentages for each level will be given.

If an elimination code 900 is attributed, then all the analyses planned to be done on the Total cohort will be done on the Total cohort without subjects with code 900, except Template 5 from EPI-DENGUE-006 BOD BR (116606) TFL (Final analysis) (14-JUN-2019) DRAFT.

The final analysis will be performed on the following study sites using data up to the specified study visits and dengue seasons covered up to study termination:

Region/Study sites name	Initial / Expansion / Replacement cohort	Subject numbers	Study visits covered up to study termination	Dengue season covered up to study termination
Rio	Initial	P - PP	Visit 1 to Visit 6	2015, 2016, 2017, 2018
	Replacement*	PP - PP	Visit 1 to Visit 4	2016, 2017, 2018
Manaus	Initial	PPD - PPD	Visit 1 to Visit 6	2015, 2016, 2017, 2018
	Replacement*	PPD - PPD	Visit 1 to Visit 2	2018
Salvador	Initial	PPD - PPD	Visit 1 to Visit 5	2016, 2017, 2018
Natal	Expansion	PPD - PPD	Visit 1 to Visit 3	2017, 2018
Campinas	Expansion	PPD - PPD	Visit 1 to Visit 2	2018

*only 1 replacement cohort

The following results will be available at the scheduled visits for the following tests:

- Dengue IgG ELISA will be available at Visit 1
- For Visit 2 onwards, Dengue IgG ELISA will be available for subjects with IgG negative at the previous visit.

The following results will be available in case of SDC, for the following tests:

Assays	Result type	Early presenters		Late presenters	
		Acute sample (first visit)	Convalescent sample (follow-up visit)	Acute sample (first visit)	Convalescent sample (follow-up visit)
RT-qPCR	Positive, negative or not typeable DENV type Copies/ml Final classification into positive or negative (used for the dengue case classification)	Yes	TNP	TNP	TNP
NS1 ELISA	Reactive or no reactive	Yes	TNP	Yes	TNP
Dengue IgM ELISA	Reactive or no reactive	Yes	Yes	Yes	Yes
Dengue capture IgG ELISA	Reactive or no reactive	TNP	Yes	Yes	Yes
Hematology / Biochemistry	Numerical results	Yes	TNP	Yes	TNP

TNP = test not performed on the sample as per protocol

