```

```

estimate 'overall' intercept 60 center 12 12 12 12 12
                        year 12 12 12 12 12
                        Month 5 5 5 5 5 5 5 5 5 5 5 5;
estimate 'overall center PPD' ' intercept 60 center 60 0 0 0 0
                        year 12 12 12 12 12
                        Month 5 5 5 5 5 5 5 5 5 5 5 5;
estimate 'overall center PPD' ' intercept 60 center 0 60 0 0 0
                        year 12 12 12 12 12
                        Month 5 5 5 5 5 5 5 5 5 5 5 5;
estimate 'overall center PPD' ' intercept 60 center 0 0 60 0 0
                        year 12 12 12 12 12
                        Month 5 5 5 5 5 5 5 5 5 5 5 5;
estimate 'overall center PPD' ' intercept 60 center 0 0 0 60 0
                        year 12 12 12 12 12
                        Month 5 5 5 5 5 5 5 5 5 5 5 5;
estimate 'overall center PPD' ' intercept 60 center 0 0 0 0 60
                        year 12 12 12 12 12
                        Month 5 5 5 5 5 5 5 5 5 5 5 5;

run;
    
```

```

data estimc; set estimc;
    if label='overall' or index(label,'overall center') then do;
        estimate=exp(lbetaestimate/60);
        lower=exp(lbetalowercl/60);
        upper=exp(lbetauppercl/60);
        end;
    else do;
        estimate=exp(lbetaestimate/12);
        lower=exp(lbetalowercl/12);
        upper=exp(lbetauppercl/12);
        end;
run;
    
```

In case of subgroup analysis by gender or by age at visit 1 (<=17years, 18-49 years and >= 50years) or in case the model does not allow estimating confidence interval (eg problem of convergence or situation where there is no event in a site, in a calendar year or in a month) CI will be computed using exact CI based on a Poisson Distribution.

The following case provides the SAS code for the exact CI for incidence rate per subject-year when there are 14 events and 400 subject-years:

```

data check;
    fu=400;
    n=14;
    Rate=n/fu;
    LL_rate= GAMINV(0.025, n)/fu;
    UL_rate= GAMINV(0.975, (n+1))/fu;
    LL_rate_=cINV(0.025, 2*n)/(2*fu);
    UL_rate_=cINV(0.975, 2*n+2)/(2*fu);
    
```

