10. CHANGES FROM PLANNED ANALYSES

All changes are provided in the additional consideration sections [7.1.2](#), [7.2.2](#), [7.3.2](#), [7.4](#) and also summarized under section [1](#).

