- Incidence rate (expressed as number of cases/1000 person-years) of laboratory-confirmed or probable symptomatic dengue infection with 95% CI for each dengue season separately: the numerator will be the total number of laboratory-confirmed or probable symptomatic dengue infections during the specific season (first of such event per subject during the specific season, using the date of first symptom onset). The denominator will be the total person-years at risk during the specific season, i.e. from the start of the specific season* until the first laboratory-confirmed or probable symptomatic dengue infection during the specific season, the end of the specific season or the subject's withdrawal, whichever comes first. Subjects withdrawn before the start of the specific season will not be included in the denominator.
- Incidence rate (expressed as number of cases/1000 person-years) of laboratory-confirmed or probable symptomatic dengue infection with 95% CI for all seasons combined: the numerator and denominator will be respectively the sum of each numerator and denominator used in the computation of incidence rate by season.
- Incidence rate (expressed as number of cases/1000 person-years) of probable symptomatic dengue infection with 95% CI for each dengue season separately: the numerator will be the total number of probable symptomatic dengue infections during the specific season (first of such event per subject during the specific season, using the date of first symptom onset). The denominator will be the total person-years at risk during the specific season, i.e. from the start of the specific season* until the first probable symptomatic dengue infection during the specific season, the end of the specific season or the subject's withdrawal, whichever comes first. Subjects withdrawn before the start of the specific season will not be included in the denominator.
- Incidence rate (expressed as number of cases/1000 person-years) of probable symptomatic dengue infection with 95% CI for all seasons combined: the numerator and denominator will be respectively the sum of each numerator and denominator used in the computation of incidence rate by season.

For calculation of incidence by age category, the time at risk will end at the day before the 18th birthday for strata $\geq 9-17$ years, and begin at the 18th birthday for strata $\geq 18-49$ years. Same rule will be applied for the other age categories.

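### Age-specific incidence is grouped by age at Visit 1 for the whole follow-up, so the age groups mix ages more the longer subjects are followed; splitting person-time at the 18th and 50th birthdays would remove this at almost no cost.

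*SAP*

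**What the plan says.** The current plan is SAP Amendment 1 (29 October 2019). Its section 7.2.2.1 sends some analyses to an exact Poisson interval and in doing so defines the age subgroups: "In case of subgroup analysis by gender or by age at visit 1 (<=17years, 18-49 years and >= 50years". Section 11.3.2 explains how age is calculated and section 11.3.3 how follow-up is counted. Neither moves a subject to another group during follow-up.

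The 14 June 2019 SAP, section 7.4, had a different rule: "For calculation of incidence by age category, the time at risk will end at the day before the 18th birthday" for the 9–17 group, with the 18–49 group starting on the birthday, and "Same rule will be applied for the other age categories". The November 2017 interim SAP, section 8.4, says the same. The protocol (section 8.5.2) speaks only of age group and gives no rule for ageing.

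Follow-up differs by cohort (SAP Amendment 1, section 7 table). Initial Rio and Manaus subjects have "Visit 1 to Visit 6" (seasons 2015–2018), and Rio replacements have "Visit 1 to Visit 4" (2016–2018). Salvador covers 2016–2018, Natal 2017–2018, and Campinas and the Manaus replacements 2018 only.

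Section 10 states: "All changes are provided in the additional consideration sections", naming 7.2.2 among them, with a summary in section 1. None of the six numbered items in that summary concerns age.

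**The concern.** A subject enrolled at 16 and followed to 20 gives all person-time, and any case, to the ≤17 group. One enrolled at 48 never reaches the ≥50 group. The share of time lived at the wrong age depends on how long the subject is followed, so a group with one label covers somewhat different ages at different sites.

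Incidence by age is a secondary objective: rates are to be estimated "in the study population by study site, gender, age-group, previous dengue exposure (primary or secondary), overall and by season". Protocol section 3.1.2 gives a use for covering all ages, namely to "validate attack rates for potential subgroups to be included in future dengue vaccine trials". Fixed age blurs the child–adult contrast that this use needs, most where follow-up is longest.

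**Working it through.** The plan gives no figure for subjects crossing an age boundary, so there is none to reproduce. The size can be worked out from the design.

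**Inputs**
- Youngest age 6 months (protocol 4.4), so the ≤17 group is 18 - 0.5 = 17.5 years wide. The 18–49 group is 50 - 18 = 32 years wide.
- Follow-up T: one year per season covered (SAP Amendment 1, section 7).
- Annual drop-out of 15–20% (protocol 8.2.1), for sensitivity only.
- Assumed, since the documents give no age distribution within groups: ages spread evenly within each group.

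**Formula.** With group width w, the mean time lived past the upper boundary is T²/(2w) per subject. Divided by T, the share of person-time at the wrong age is T/(2w). The share of subjects who cross is T/w.

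| T (years) | Cohorts | ≤17 lived at 18+ (T/35) | 18–49 lived at 50+ (T/64) |
|---|---|---|---|
| 4 | Initial Rio, Manaus | 11.4% | 6.3% |
| 3 | Salvador, Rio replacements | 8.6% | 4.7% |
| 2 | Natal | 5.7% | 3.1% |
| 1 | Campinas, Manaus replacements | 2.9% | 1.6% |

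At four years, 4/17.5 = 22.9% of the ≤17 subjects and 4/32 = 12.5% of the 18–49 subjects cross.

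**Sensitivity at four years**
- With 15% to 20% annual drop-out, the ≤17 share falls to 10.2% to 9.7%, and the 18–49 share to 5.6% to 5.3%.
- If the density of ages near 18 is half or twice the even one, the ≤17 share is 5.7% or 22.9%.

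**Effect on the rate.** With share s at the wrong age and adult-to-child rate ratio k, the reported ≤17 rate divided by the true under-18 rate is 1 - s + s·k. For s = 0.114:
- k = 0.5 gives 0.943 (about -6%).
- k = 2 gives 1.114 (about +11%).

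For one year (s = 0.029) the same ratios give about -1% and +3%. The values of k are assumptions.

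**Against the sampling error.** The SAP's own exact-interval example (14 events, 400 subject-years) has a rate of 0.0350 and limits of 0.0191 and 0.0587. Those are about -45% and +68% of the rate, several times the bias above.

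**By follow-up year.** In year t the ≤17 share is (t - 0.5)/17.5: 2.9%, 8.6%, 14.3% and 20.0% in years 1 to 4. If age-specific rates are also shown by calendar year, the mixing in the last year at Rio and Manaus exceeds the pooled 11.4%.

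**The case against.** The strongest case is that age at Visit 1 is a valid grouping, stated as such, and the one used in the demographic table (section 7.1.2), so that subgroup sizes and rates share a definition. A future trial also enrols people at an entry age and then follows them. The June 2019 SAP used six narrow groups, where a birthday split could hardly be avoided; three wide groups need it less. Events are few, all analyses are descriptive, and the sponsor has ended its dengue vaccine development. All of this supports a low priority. It does not remove the mixing: with three groups the share still rises with follow-up, and the split is no harder to program.

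Two stronger readings are tempting.

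A reader might infer that initial subjects are affected and replacements hardly at all. The section 7 table does not support this. Rio replacements cover the same three seasons as Salvador's initial cohort, and Campinas, an expansion site, has the same single season as the Manaus replacements. Length of follow-up drives the effect.

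A reader might also infer that the change was hidden. The new grouping is written in 7.2.2.1, which lies within a section that section 10 names as a place for changes. The protocol fixed no ageing rule, and differing from a superseded SAP is not in itself an error. What stands is that the section 1 summary omits the change and no reason is given for it.

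**Conclusion.** The concern holds in a limited form. Under the current rule about 3% to 11% of ≤17 person-time, and 2% to 6% of 18–49 person-time, is lived past the upper age limit, rising with length of follow-up. These shares assume evenly spread ages, one year per season and no drop-out.

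The possible bias of -6% to +11% applies to the four-year ≤17 rate only and also rests on an assumed rate ratio between one half and two. Rates pooled over sites would be affected less, because they mix in shorter follow-up.

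It would be wrong to infer that the age-specific rates are unusable. The bias will usually be smaller than the width of the Poisson interval, and the primary overall rate does not depend on the grouping. This is an avoidable imprecision in a secondary, descriptive result. The earlier SAP versions matter only because they show that the sponsor regarded the split as feasible.

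**What to change.** In SAP section 7.2.2.1 keep the three groups but define them by attained age. End person-time in ≤17 the day before the 18th birthday and start 18–49 on that birthday; do the same at 50. Assign each case by age at onset, using the case start date already defined in section 6.1. Keep age at Visit 1 for the demographic table, and add one line on the age rule to the section 1 summary.

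If the sponsor prefers age at Visit 1, the least needed is to give the reason, list the change in section 1 and head the incidence tables as age at enrolment.

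The cost is a few words of SAP text and a person-time split that the sponsor had already specified. It needs only dates of birth, follow-up and onset, so no new data.

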2. STUDY DESIGN

2.1. Study design overview

- **Type of design:** Prospective, multicenter, community-based, household-sampling, cohort study in Brazil.
- **Duration of the study:** The study period per initial site, initially planned to be one year, was planned to be extended by additional three years (overall four years) to cover three additional dengue seasons. The study period for any new site was planned to be 3 years.
- **Enrolment wave:** There were 2 waves of enrolment for recruiting the planned 3600 subjects:
 - Initial Cohort = about 1800 subjects planned – four years follow-up planned – INITIAL sites: Rio (PPD), Manaus (PPD) and Salvador (PPD).
 - Expansion Cohort = about 1800 subjects planned – three years follow-up planned – planned NEW sites: Natal (PPD), Campo Grande (PPD), and Campinas (PPD).
- **Replacement:** replacement subjects were enrolled in order to compensate for subjects who did not wish to extend their participation for three additional years (for subjects from the initial cohorts), subjects who prematurely terminated participation or subjects who were lost to follow-up (for subjects from the initial and expansion cohorts).
- This was done to maintain a cohort size of at least 500 subjects per site, in the initial and expansion cohorts, at the beginning of each additional study year/season.

• **Schematic representation of the scheduled visits:**

V=Visit

The scheduled visits for initial cohort subjects are shown in black

New enrolments were to be done yearly (as needed) till the end of study Year 3 of each study site

Enrollment of expansion cohort subjects started preferably during study Year 2

For replacement subjects, the number of visits depended on the year enrolled

- **Type of study:** self-contained.
- **Data collection:** Electronic Case Report Form (eCRF).
- **Study termination:** in December 2017, GSK decided to deprioritise the development of the dengue purified inactivated vaccine (DPIV) candidate and to terminate the study EPI-DENGUE-006 at the study visit planned after the 2018 dengue season. This decision was made due to the scientific challenges and development risks associated with the candidate vaccine. The planned study site in Campo Grande was not initiated before the decision of study termination was taken, so no subjects were enrolled in that site.

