2.4. Dengue seasons

Dengue season:

Region/study site name (site number)	Dengue season
Rio (PPD)	1st January to 30th June
Manaus (PPD)	1st January to 30th June
Salvador (PPD)	1st January to 30th June
Natal (PPD)	1st January to 30th June
Campinas (PPD)	1st January to 30th June

3. OBJECTIVES**3.1. Primary objective**

- To estimate the incidence of laboratory-confirmed symptomatic dengue infection in the study population by year/season.

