7.2.2. Additional considerations

7.2.2.1. Incidence rate

In light of the low number of dengue episodes, the large number of positive anti-dengue IgG at visit 1 and the number of dengue cases reported outside the season,

1. The analyses of PCR confirmed cases (only 10 cases) and the analyses of secondary dengue infections were removed.
2. The analyses by seroprevalence at each visit were removed,
3. The analyses by season were removed. Only the analyses by calendar year are to be conducted

- 4. Subjects without seroprevalence status at visit 1 were removed from the ATP cohort because serological status of symptomatic/inapparent dengue infections cannot be assessed properly for such subjects
- 5. Planned analyses of medical and vaccination history were removed.
- 6. The statistical method was updated to ignore the household cluster effect and to provide incidence rate with confidence interval in absence of dengue episodes in a calendar year for a study site .

Regarding the last point, the expected annual incidence rate for a cohort of subjects followed over a full calendar will be computed using a log-linear model with the number of dengue events (all cases) as depend variable and the total number of subject-month as offset. The model will include the study site, year and month as independent categorical fixed effects (see below).

The expected annual incidence rate in a study site for each year will be estimated as the average of incidence rate over months

```

proc genmod ;
  class center month year;
  model evt= center year month /
    dist=poisson link=log offset=ln TYPE3;

  ods output Estimates=estimc;
  estimate 'center PPD 2014' intercept 12 center 12 0 0 0 0
    year 12 0 0 0 0
    Month 1 1 1 1 1 1 1 1 1 1 1;
  estimate 'center PPD 2014' intercept 12 center 0 12 0 0 0
    year 12 0 0 0 0
    Month 1 1 1 1 1 1 1 1 1 1 1;
  estimate 'center PPD 2014' intercept 12 center 0 0 12 0 0
    year 12 0 0 0 0
    Month 1 1 1 1 1 1 1 1 1 1 1;
  estimate 'center PPD 2014' intercept 12 center 0 0 0 12 0
    year 12 0 0 0 0
    Month 1 1 1 1 1 1 1 1 1 1 1;
  estimate 'center PPD 2014' intercept 12 center 0 0 0 0 12
    year 12 0 0 0 0
    Month 1 1 1 1 1 1 1 1 1 1 1;
  estimate 'overall 2014' intercept 12 center 2.4 2.4 2.4 2.4 2.4
    y 12 0 0 0 0
    Month 1 1 1 1 1 1 1 1 1 1 1;
  estimate 'center PPD 2015' intercept 12 center 12 0 0 0 0
    year 0 12 0 0 0
    Month 1 1 1 1 1 1 1 1 1 1 1;
  estimate 'center PPD 2015' intercept 12 center 0 12 0 0 0

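### The exact-Poisson fallback gives crude rates over partly observed calendar years, so under January-June seasonality its non-zero rates run low in each site's first year and high in 2018

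*SAP*

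**What the plan says.** All references are to SAP Amendment 1 unless stated.

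- **Target.** Section 7.2.2.1 says that "the expected annual incidence rate for a cohort of subjects followed over a full calendar will be computed using a log-linear model" (the word year is evidently missing), with site, year and month as fixed effects. By-season analyses are dropped, so the calendar year is the only reporting period.
- **Fallback, first trigger.** "In case of subgroup analysis by gender or by age at visit 1", the model is not used at all.
- **Fallback, second trigger.** It is also not used when it cannot give an interval, for example through non-convergence or a "situation where there is no event in a site, in a calendar year or in a month". In either case "CI will be computed using exact CI based on a Poisson Distribution".
- **Fallback code.** It is introduced as the "exact CI for incidence rate per subject-year when there are 14 events and 400 subject-years". It sets the rate to events over follow-up, with limits such as "LL_rate= GAMINV(0.025, n)/fu". It has no month term, no weighting and no full-year condition.
- **Follow-up.** Section 11.3.3 counts actual follow-up days, so only observed months enter the denominator.
- **Season.** Section 2.4 gives "1st January to 30th June" for all five sites.
- **Coverage.** The table in section 7 lists the first season covered as 2015 (Rio, Manaus), 2016 (Salvador), 2017 (Natal) and 2018 (Campinas). Section 2.2.4 says recruitment was preferably outside the peak. Section 2.1 says the decision was "to terminate the study EPI-DENGUE-006 at the study visit planned after the 2018 dengue season".

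**The concern.** The model puts month in so that a partly observed year can still be expressed as a full-year rate. The fallback drops that adjustment without saying that the quantity has changed.

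The years most affected are built into the design. A site whose first covered season is 2015 but which has a 2014 estimate must have its 2014 follow-up mainly in July-December. By the same reasoning the partial first years are 2014 for Rio and Manaus, 2015 for Salvador, 2016 for Natal and 2017 for Campinas. At the other end, follow-up stops some time after June 2018, so January-June is over-represented in that year.

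The primary objective is incidence by year/season. Where the fallback supplies a yearly rate, a reader comparing years could take a change in which months were observed for a change in dengue incidence.

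**Working it through.** **Inputs from the documents.** January-June season (2.4); seasons covered by site (7); follow-up in observed days (11.3.3); stop after the 2018 season (2.1); an illustrative incidence of 9 per 1000 person-years (Protocol 8.2.3).

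**Assumptions.** The share s of a year's cases falling in January-June is not given; I use 50% to 90%. The month in which follow-up ended in 2018 is not given; I use June, August, September and December. The rate is taken as flat within each half-year.

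**Check of the interval formula.** The gamma limits for 30 cases in 3322.7 person-years are 6.1 to 12.9 per 1000, which matches the exact interval in Protocol Table 15. (Among the rows checked, small-count rows differ by up to 0.5, which does not matter here.) The SAP's own example, for which no result is printed, gives 14/400 = 35.0 per 1000 (19.1 to 58.7). The interval code does what it says; the issue is the rate it is attached to.

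**Bias of the crude rate.** Let R be the true annual rate. The January-June rate is 2sR and the July-December rate is 2(1-s)R.

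- First year, July-December only: ratio to R = 2(1-s), whatever the start month within that half.
- 2018, with k months observed after June: ratio = [s + (1-s)k/6] / (0.5 + k/12).

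| s | First year | 2018 to June | to August | to September | to December |
|---|---|---|---|---|---|
| 50% | 1.0 | 1.0 | 1.0 | 1.0 | 1.0 |
| 60% | 0.8 | 1.2 | 1.1 | 1.07 | 1.0 |
| 70% | 0.6 | 1.4 | 1.2 | 1.13 | 1.0 |
| 80% | 0.4 | 1.6 | 1.3 | 1.2 | 1.0 |
| 90% | 0.2 | 1.8 | 1.4 | 1.27 | 1.0 |

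**Illustration.** Take s = 80%, follow-up from September of the first year to September 2018, and a constant true rate of 9.0 per 1000. A site's first year shows 0.4 × 9.0 = 3.6, full years show 9.0, and 2018 shows 1.2 × 9.0 = 10.8.

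Pooled over five sites of equal size, the yearly rates for 2014 to 2018 are 3.6, 8.2, 8.5, 8.6 and 10.8. For 2015, for example, (24 × 9.0 + 4 × 3.6)/28 = 8.2.

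All years together contain 84 in-season site-months (24 + 24 + 18 + 12 + 6) at 14.4 and 89 off-season site-months (25 + 25 + 19 + 13 + 7) at 3.6. That gives (84 × 14.4 + 89 × 3.6)/173 = 8.8, or 0.98 of the true rate.

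**How often an empty month would trigger the fallback.** Give each in-season month probability s/6 and each off-season month (1-s)/6, with even follow-up. Inclusion-exclusion then gives the chance that at least one of the 12 calendar months has no event:

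| Events | s = 60% | s = 70% | s = 80% |
|---|---|---|---|
| 30 | 70% | 83% | 95% |
| 60 | 10% | 25% | 58% |
| 100 | 1% | 4% | 19% |

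Every estimate statement in the code puts weight on all 12 months, so one empty month affects every model cell.

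**The model as benchmark.** The code averages log rates and then exponentiates, which returns a geometric mean. Its ratio to R is 2√(s(1-s)), or 0.8 at s = 80%: 7.2 instead of 9.0. The SAP text describes an average of the monthly rates. Crude and model rates therefore differ even in a fully observed year, and there the crude rate is the correct one.

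**The case against.** The strongest reply has five parts.

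1. **The sentence concerns only the interval, and its unit is per subject-year, not annual.** Events over person-time at risk is also the protocol's own definition of the primary rate (8.5.2). This stands as to wording, so a reader who infers that the crude formula is wrong in itself goes too far. The code does supply a crude point estimate, however, and the section's stated aim is the full-year rate. Pairing a model estimate with the exact interval would not help, because the two would describe different quantities.
2. **The trigger that the SAP gives as its motive is a site-year without episodes.** There the rate is zero under any weighting. This stands: only the upper limit is affected.
3. **Model and fallback cells need not sit side by side.** A reader might infer mixed methods throughout one table. With an empty month, all model cells fail together and all become crude. Mixing is mainly a matter of pooled yearly rows when a site is empty, and of subgroup tables against main tables. Whether subgroup tables are split by year depends on table templates that are not in the documents.
4. **The size is unknown.** The SAP itself cites dengue cases outside the season as a reason for dropping season analyses, and at s = 50% there is no bias. Enrolment and last-visit dates are not given. The number of events entering the model is not given either; the 10 mentioned are PCR-confirmed cases only. All of this stands and is why ranges are shown.
5. **All analyses are descriptive, and the all-years rate is nearly unbiased.** This stands. The effect is confined to yearly rates at the two ends.

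**Conclusion.** The mismatch between target and fallback is real. In partly observed years the fallback does not estimate the annual rate that section 7.2.2.1 sets out to report. If in-season incidence exceeds off-season incidence, non-zero fallback rates are biased low in each site's first calendar year and high in 2018.

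For s from 50% to 90% the first-year ratio runs from 1.0 to 0.2. At s = 80% the 2018 ratio is 1.6, 1.3, 1.2 or 1.0 for follow-up ending in June, August, September or December.

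The conclusion rests on two inferences: that first years are mainly July-December, drawn from the seasons-covered table, and that 2018 follow-up ended before 31 December.

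A reader might go further and infer that the reported yearly rates show a false rise of a known size, or that overall incidence is misestimated. The documents support neither. The threefold contrast between 3.6 and 10.8 depends on the assumed share and dates, the pooled rates for 2015 to 2017 are almost flat, and rates over all years combined are largely unaffected.

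**What to change.** - **Fallback rate.** Compute the annual rate as the equally weighted arithmetic average of the January-June and July-December rates, with a gamma-type exact interval for a weighted sum of Poisson counts. Apply this to any gender or age tables by year as well.
- **Empty months.** First refit the model with month collapsed to season and off-season. Average the fitted rates arithmetically, not on the log scale, in all model estimates, so that model and fallback cells describe the same quantity.
- **Empty site or year.** Collapsing months does not help here, so go straight to the weighted-rate interval. State that the lower limit is zero when there are no events, because the printed gamma code is undefined at n = 0.
- **Half-years.** Where a site-year has only off-season time, print it as a July-December rate and do not present it as annual.
- **Labelling.** Flag fallback cells and partly observed years in the tables, and give the months covered.

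The cost is SAP wording, a short program and slightly wider intervals. The data needed are already held.
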